8.1 Visit Schedule

During the trial 6 regular trial visits are scheduled.

A **Screening Visit** (Day -28 to -8) will be performed to decide about the patient's eligibility for trial participation. Once the patient gave his/her informed consent he/she will complete the Insomnia Severity Index (ISI) questionnaire on **AMS-ePRO®**. A urine and breath alcohol test will be conducted on drugs and alcohol.

The following procedures will be performed:

- Obtain written informed consent from the patient (section 12.4)
- Completion of ISI on **AMS-ePRO®** (section 9.1.14)
- Diagnosis of short-term insomnia based on DSM-5
- Check if patient agrees to continuously (day and night) wear the actimetric device on the wrist (section 9.1.5)
- Check applicable eligibility criteria (inclusion and exclusion criteria, section 6.1 and 6.2)
- Documentation of demographics
- Documentation of medical history and concomitant diseases
- Documentation of concomitant medication
- Physical examination (section 9.2.3)
- Assessment of vital signs (heart rate, systolic/ diastolic blood pressure) (section 9.2.2)
- Collection of 8.4 ml blood for safety laboratory analyses (complete blood count (CBC) with differential, thyroid hormones, blood glucose, C-reactive protein (CRP), erythrocyte sedimentation rate (ESR), liver enzymes (aspartate aminotransferase [ASAT], alanine transaminase [ALAT], gamma-glutamyl transferase [gamma GT], alkaline phosphatase), (section 9.2.4)
- Urine pregnancy test in women with childbearing potential (section 9.1.12)
- Urine collection for test on drugs (section 9.1.11)
- Breath alcohol test (section 9.1.11)

- Adverse Event recording from Screening Visit onwards (starting with written informed consent) until End of Trial (section 9.2.1).
- Instruction in the use of the actigraphy watch, i.e., Actiwatch Spectrum Plus, and its handing over.

From Screening Visit onwards daily until the End of Trial (Follow-up Visit/ Day 28+3) patients must wear an actigraphy watch recording their sleeping and activity cycles, complete a sleep diary and answer digital questionnaires regarding stress level (**AMS-ePRO®**).

At **Baseline 1** (Day -2 to Day -1) patients will have their first night at the trial site for PSG adaptation and screening for exclusion criterion 3. Patients complete their electronic sleep diary (adapted from DGSM, on **AMS-ePRO®**) to be kept until the End of Trial (Follow-up Visit/ Day 28+3) and questionnaires on sleep, mood, stress and quality of life. In the evening before the Baseline 1 night urine and breath alcohol tests will be conducted on drugs and alcohol, respectively. After awakening (Day -1) resting state stress parameters in saliva are to be collected (at 5 time points) and every 3 hours (at 4 time points). In the course of the morning, patients will perform neuropsychological tests from the TAP battery. An rsEEG and measurement of resting heart rate and HRV will be performed at approximately 15 minutes prior CPT. Around 12:00 at Day -1 a CPT will be conducted, before and afterwards blood samples will be collected. Patients will complete a subjective pain and stress rating during CPT test.

The following procedures will be performed:

- Urine collection for test on drugs in the evening at Day -2 (section 9.1.11)
- Breath alcohol test in the evening at Day -2 (section 9.1.11)
- Completion of the following questionnaires:
 - a) on paper: BAI, BDI-II, WEIMuS, PSQI, PSS-10, SF-36v2, SSQ-25
 - b) on **AMS-ePRO®**: ESS, ISI, PASA (section 9.1.14)
- PSG for screening of exclusion criterion 3 and for adaptation to the unfamiliar sleep lab environment in the night between Day -2 and Day -1 (section 9.1.1)
- Check exclusion criterion 3 at Day -1
- Collection of 0.5 to 1 ml saliva to measure cortisol, DHEA-S and alpha-amylase at awakening (0 minutes), and after 15 minutes, 30 minutes, 45 minutes, 60 minutes, 3 hours, 6 hours, 9 hours and 12 hours after awakening at Day -1 (section 9.1.2)
- Neuropsychological tests (TAP) at Day -1 (section 9.1.10)
- Resting state EEG, resting state HR and HRV to measure daytime performance at Day -1 (section 9.1.3)
- CPT around 12:00 including subjective pain rating and pain tolerance, heart rate and associated HRV measures, electrodermal activity, and EEG at Day -1 (section 9.1.7)
- Collection of approximately 12.5 ml blood for measuring cortisol, DHEA-S, adrenaline, noradrenaline, inflammation markers (IL-6 and TNF- α) prior to CPT, 20 minutes and 50 minutes after CPT at Day -1 (section 9.1.8)
- Adverse events at Day -2 (section 10)
- Changes in concomitant medication at Day -2
- Complete sleep diary and stress assessment (in **AMS-ePRO®**).

At **Baseline 2** (Day -1 to Day 0) patients will stay at the site for a second night for PSG. After awakening (Day 0) resting state stress parameters in saliva are to be collected (at 5 time points). Patients will be randomly assigned to treatment group Neurexan® or Placebo with a 1:1 allocation and stratification by sex.

The following procedures will be performed:

- Urine collection for test on drugs in the evening at Day -1 (section 9.1.11)
- Breath alcohol test in the evening at Day -1 (section 9.1.11)
- Baseline 2 PSG night to measure primary, i.e., SE and secondary endpoints, i.e., SOL, WASO, TST, NWAK, and ARI during sleep in the night between Day -1 and Day 0 (section 9.1.1)
- Collection of 0.5 to 1 ml saliva to measure cortisol, DHEA-S and alpha-amylase at awakening (0 minutes), and at 15 minutes, 30 minutes, 45 minutes, 60 minutes after awakening at Day 0 (section 9.1.2)
- Adverse events at Day -1 and Day 0 (section 9.2.1)
- Changes in concomitant medication at Day -1 and Day 0
- Randomization to treatment group at Day 0 (section 11.2)
- Distribution of IMP and instruction regarding use of IMP at Day 0
- Starting IMP treatment after having performed all Baseline 2 assessments at midday Day 0 (section 7.1)
- Complete sleep diary and stress assessment (in **AMS**-ePRO®).

Patients will continue to take their trial treatment for 14 consecutive days (Day 0 - Day 13).

At **Visit 1** (Day 12 to Day 13; +2 days) patients return to the trial site for another PSG adaptation night. A urine and breath alcohol test will be conducted on drugs and alcohol, respectively. After awakening (Day 13) resting state stress parameters in saliva are to be collected (at 5 time points) and every 3-hours (at 4 time points). In the course of the morning, patients will perform neuropsychological tests from the TAP battery. An rsEEG and measurement of resting heart rate and HRV and EDA will be performed at approximately 15 minutes prior CPT. Around 12:00 at Day 13 a CPT will be performed, blood samples will be collected (before CPT and 20 minutes and 50 minutes after CPT) and patients will complete a subjective pain and stress rating. During CPT an EEG will be performed and heart rate and HRV will be measured. Additionally, patients will complete questionnaires on sleep, stress and quality of life on paper (BDI-II, WEIMuS) and on **AMS**-ePRO® (ESS, ISI, PASA).

The following procedures will be performed:

- Urine collection for test on drugs in the evening at Day 12 (section 9.1.11)
- Breath alcohol test in the evening at Day 12 (section 9.1.11)
- PSG night, again for adaptation to the unfamiliar sleep lab environment between Day 12 and Day 13 (section 9.1.1)
- Collection of 0.5 to 1 ml saliva to measure cortisol, DHEA-S and alpha-amylase at awakening (0 minutes), and at 15 minutes, 30 minutes, 45 minutes, 60 minutes, 3 hours, 6 hours, 9 hours and 12 hours after awakening at Day 13 (section 9.1.2)
- Neuropsychological tests (TAP) at Day 13 (section 9.1.10)

- Resting state EEG, resting state HR and HRV to measure daytime performance at Day 13 (section 9.1.3)
- CPT around 12:00 including subjective pain and stress rating, heart rate and associated HRV measures, electrodermal activity, and EEG at Day 13 (section 9.1.7)
- Collection of approximately 12.5 ml blood for measuring cortisol, DHEA-S, adrenaline, noradrenaline, inflammation markers (IL-6 and TNF- α) prior to CPT, 20 minutes and 50 minutes after CPT at Day 13 (section 9.1.8)
- Completion of the following questionnaires: ESS, ISI, PASA (**AMS-ePRO[®]**); BDI-II and WEIMuS (both paper-based; section 9.1.14)
- Adverse events at Day 12 (section 9.2.1)
- Changes in concomitant medication at Day 12
- Complete sleep diary and stress assessment (in **AMS-ePRO[®]**).

At **Visit 2** (Day 13 to Day 14; + 2 days but on the next day after Visit 1) patients will stay at the site for a second night for PSG. After awakening (Day 14) resting state stress parameters in saliva are to be collected (at 5 time points).

The following procedures will be performed:

- Urine collection for test on drugs in the evening at Day 13 (section 9.1.11)
- Breath alcohol test in the evening at Day 13 (section 9.1.11)
- Last IMP intake in the night of Day 13 prior to sleep
- PSG recording to measure SOL, WASO, TST, NWAK, and arousal indices during sleep in the night between Day 13 and Day 14 (section 9.1.1)
- Collection of 0.5 to 1 ml saliva to measure cortisol, DHEA-S and alpha-amylase at awakening (0 minutes), and at 15 minutes, 30 minutes, 45 minutes, 60 minutes after awakening at Day 14 (section 9.1.2)
- Adverse events at Day 13 and Day 14 (section 9.2.1)
- Changes in concomitant medication at Day 13 and Day 14
- Complete sleep diary and stress assessment (in **AMS-ePRO[®]**)
- Return of IMP.

At **Follow-up Visit** (Day 28; + 3 days) patients will have one last Visit at the trial site to complete questionnaires on sleep, stress and quality of life (BAI, PSQI, PSS-10, SF-36v2, SSQ-25, based on paper). Patients will complete their electronic sleep diary (**AMS-ePRO[®]**) and return their portable actimetric device.

- Completion of the following paper-based questionnaires (BAI, PSQI, PSS-10, SF-36v2, SSQ-25)
- Completion of the last daily sleep diary and stress assessment (**AMS-ePRO[®]**)
- Return of portable actimetric device
- Adverse events between Visit 2 and until Follow-up Visit (section 9.2.1)
- Changes in concomitant medication between Visit 2 and Follow-up Visit.

Following all above-mentioned procedures including the Follow-up Visit (Day 28 + 3 days) to collect patient-reported outcomes on questionnaire, the End of Trial (EoT) documentation will be completed.

The EoT documentation is also to be completed in the electronic Case Report Form (eCRF) in the event of premature termination/ discontinuation, with reasons to be given (section 6.3).

Table 3: Flowchart of Trial Procedures

Procedure	Run-In (9 to 29 days)			Treatment (14 days)		Follow -Up (14 days)
	Screening Visit Day -28 to -8	Baseline 1 Day -2 to -1	Baseline 2 Day -1 to 0	Visit 1 Day 12 to 13 +2 days [^]	Visit 2 Day 13 to 14 +2 days [^]	
Diagnosis according to DSM-5 (short-term insomnia)	X					
Inclusion/ Exclusion Criteria (except exclusion criterion 3)	X					
Exclusion Criterion 3		X				
Patient Information/ Informed Consent	X					
Demographics ^o	X					
Randomization				X		
Vital Signs (heart rate, systolic/ diastolic blood pressure)	X					
Physical Examination	X					
Safety Laboratory (CBC with differential, thyroid hormones, blood glucose, CRP, ESR, liver enzymes)		X				
Urine Pregnancy Test	X					
Medical History and Concomitant Diseases	X					
Urine Drug Test	X	X	X	X	X	
Breath Alcohol Test	X	X	X	X	X	
Adverse Events (AEs)	X				X	
Concomitant Medications	X				X	
Investigational Treatment (Neurexan [®] / Placebo)			X [*]	X	X	
Return of IMP						X
Polysomnography (PSG) Parameters		X adaptation (‘screening’)	X	X adaptation	X	
Pittsburgh Sleep Quality Index (PSQI), Paper PRO		X				X
Sleep Diary ^{oo} (adapted from DGSM), AMS-ePRO [®]	X	X	X	X	X	X
Insomnia Severity Index (ISI), AMS-ePRO [®]	X	X		X		
Resting State EEG (rsEEG)		X		X		

Procedure	Run-In (9 to 29 days)			Treatment (14 days)		Follow-Up (14 days)
	Screening Visit Day -28 to -8	Baseline 1 Day -2 to -1	Baseline 2 Day -1 to 0	Visit 1 Day 12 to 13 +2 days [^]	Visit 2 Day 13 to 14 +2 days [^]	
Resting Heart Rate (HR) and Heart Rate Variability (HRV), and Electrodermal Activity (EDA)		X		X		
Daytime Performance Questionnaires, Level of Anxiety and Depression Paper PROs: BAI, BDI-II, WEIMuS, SF-36v2 AMS-ePRO [®] : ESS		X		X BDI-II, ESS, WEIMuS		X BAI, SF-36v2
Actigraphy	X	X	X	X	X	X
Stress Questionnaires Paper PROs: PSS-10, SSQ-25 AMS-ePRO [®] : PASA		X		X PASA		X PSS-10, SSQ-25
AMS-ePRO [®] Questionnaires to measure daily stress levels (EMAs)	X	X	X	X	X	X
Resting State Stress Response based on Saliva Biomarkers after Awakening and During the Day [#]		X	X	X	X	
Stress Responses induced by Cold Pressor Test (CPT) ¹ as assessed with EEG, HR, HRV and EDA		X		X		
Neuropsychological Tests (TAP)		X		X		
End of Trial (EoT) Documentation ²						X

Abbreviations: AE - Adverse Event, BAI - Beck's Anxiety Inventory (paper PRO), BDI-II - Beck's Depression Inventory revision II (paper PRO), CBC - Complete Blood Count, CPT - Cold Pressor Test, CRP - C-reactive protein, DGSM - Deutsche Gesellschaft für Schlaforschung und Schlafmedizin, DHEA-S - dehydroepiandrosterone sulfate, DSM-5 - Diagnostic and Statistical Manual of Mental Disorders, 5th edition, EDA - Electrodermal Activity, EEG - electroencephalogram, EMAs - Ecological Momentary Assessments (used for daily stress assessment via **AMS-ePRO[®]**), EoT - End of Trial, (e)PRO - (electronic) Patient-Reported Outcome, ESR - Erythrocyte Sedimentation Rate, ESS - Epworth Sleepiness Scale (**AMS-ePRO[®]**), HR - Heart Rate, HRV - Heart Rate Variability, IMP - Investigational Medicinal Product, ISI - Insomnia Severity Index (**AMS-ePRO[®]**), min - minutes, ml - milliliters, PASA - Primary Appraisal Secondary Appraisal (**AMS-ePRO[®]**), PRO - Patient-Reported Outcome, PSG - polysomnography; PSQI - Pittsburgh Sleep Quality Index (paper PRO), PSS-10 - Perceived Stress Scale-10 (paper PRO), rsEEG - resting state electroencephalography, SF-36v2 - Short Form-36 version 2.0 (paper PRO), SSQ-25 - Subclinical Stress Symptom Questionnaire-25 (paper PRO), TAP - Test of Attentional Performance, WEIMuS - Würzburg Fatigue Inventory (paper PRO).

[^]Visit 1 may be performed on Day 12+2 days. In any case, Visit 1 and Visit 2 will be performed on two consecutive days.

^{##}Follow-up Visit may be performed on Day 28 +3 days.

◦ Demographics include sex, height and weight.

* Starting IMP treatment after having performed all Baseline 2 assessments and after randomization at midday Day 0 for 14 consecutive days (+ maximum 2 days allowance) until Visit 2 (Day 13).

◦◦ Sleep diary will be completed daily; starting at Screening Visit until End of Trial

Stress biomarkers in saliva: cortisol, alpha-amylase, dehydroepiandrosterone sulfate (DHEA-S) at 5 time points: after awakening from PSG nights at Baseline 1/ Day -1, Baseline 2/ Day 0, Visit 1/ Day 13 and Visit 2/ Day 14 collection of around 0.5 to 1 ml saliva at 0 minutes, 15 minutes, 30 minutes, 45 minutes, 60 minutes (5 time points) for the assessment of Cortisol Awakening Response (CAR) and additionally at Baseline 1/ Day -1 and Visit 1/ Day 13 diurnal profile of stress biomarkers by collecting saliva samples at 3-hourly intervals over 12 hours (4 time points) synchronized to the awakening time.

¹ Including subjective pain rating and pain tolerance, blood sampling before CPT, 20 minutes and 50 minutes after CPT to assess biomarkers cortisol and DHEA-S, adrenalin, noradrenalin and inflammatory response (IL-6 and TNF- α), autonomic and cortical stress response (heart rate, HRV, electrodermal activity (EDA) and EEG).

² In case of premature discontinuation reason to be given.

9. Efficacy and Safety Parameters

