- Questionnaires: Epworth Sleepiness Scale (ESS), Würzburg Fatigue Inventory (WEIMuS) and Beck's Depression Inventory-II (BDI-II) at Visit 1 compared to Baseline 1, and Quality of Life (QoL) by QoL questionnaire Short Form-36 version 2.0 (SF-36v2) and Beck's Anxiety Inventory (BAI) at Follow-Up Visit compared to Baseline 1
- Neuropsychological tests assessing general cognitive functioning, alertness, vigilance, and sustained attention: three subtests from electronic Tests of Attentional Performance (TAP) test battery at Visit 1 compared to Baseline 1.

Stress Processing

Given the reported HPA axis dysregulation in the form of an altered cortisol secretion pattern in insomnia patients, a secondary outcome is to demonstrate changes in decreased resting state stress parameters in saliva as well as stress reactivity to physiological challenge using the Cold Pressor Test (CPT) in terms of changes in serum levels of cortisol in short-term insomnia patients treated with Neurexan®.

- Resting state stress response by
 - Changes in stress biomarkers in saliva compared to baseline
 - Cortisol
 - Alpha-amylase
 - Dehydroepiandrosterone sulfate (DHEA-S)
 - Time course of stress biomarkers release synchronized to the awakening time (5 time points after awakening: 0 minutes, 15 minutes, 30 minutes, 45 minutes, 60 minutes for the assessment of Cortisol Awakening Response (CAR))
 - Diurnal profile of stress biomarkers by collecting saliva samples at 3-hourly intervals over 12 hours (4 time points) synchronized to the awakening time.
- Stress response induced by CPT
 - Changes in subjective pain rating and pain tolerance at Visit 1 compared to Baseline 1

Blood sampling

- Changes in the cortisol time course: Visit 1 before CPT, 20 minutes, and 50 minutes after CPT compared to Baseline 1
- Changes in dehydroepiandrosterone sulfate (DHEA-S) time course: Visit 1 before CPT, 20 minutes, and 50 minutes after CPT; Visit 1 compared to Baseline 1
- Changes in the time course of adrenalin, noradrenalin and the inflammatory response (IL-6 and TNF- α): Visit 1 before CPT, 20 minutes, and 50 minutes after CPT compared to Baseline 1.

Autonomic stress response:

- Changes in heart rate and associated HRV measures, electrodermal activity (EDA); Visit 1 compared to Baseline 1.

EEG stress response:

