9.1.2 Resting State Stress Response

Resting state stress response will be assessed based on the stress biomarkers cortisol, alpha-amylase and dehydroepiandrosterone sulfate (DHEA-S) in saliva samples.

Around 0.5 to 1 ml of saliva are to be collected at each of 5 time points starting immediately after awakening from PSG adaptation nights (Baseline 1/ Day -1 and Visit 1/ Day 13) and PSG nights (Baseline 2/ Day 0 and Visit 2/ Day 14) followed by sampling at 15 minutes, 30 minutes, 45 minutes and 60 minutes after awakening for the assessment of Cortisol Awakening Response (CAR).

To assess a diurnal profile of stress markers 4 additional saliva samples (around 0.5 to 1 ml/ sample) are to be collected at 4 time points at 3-hourly intervals over 12 hours at Baseline 1/ Day -1 and Visit 1/ Day 13 (Table 4).

Table 4: Resting state saliva sampling

Cortisol Awakening Response					Diurnal Profile*			
After awakening	+15 min	+30 min	+45 min	+60 min	+3 h	+6 h	+9 h	+12 h
X	X	X	X	X	X	X	X	X

*Only at Baseline 1 and Visit 1.

Saliva samples are collected in 2 ml SaliCap sampling tubes (TECAN/ IBL International, Hamburg, Germany, ref. no. RE69985) using short drinking straws. One sample of 0.5 to 1 ml saliva is sufficient to analyze cortisol, alpha-amylase and DHEA-S.

After instruction by the site personnel, samples are collected independently by each trial participant. Salivary samples are stored frozen at -80°C (+/- 10°C fluctuation) for interim storage (approximately 3 months) at the biobank of the local laboratory of the investigational site (Institut für Klinische Chemie und Laboratoriumsdiagnostik, IKCL, Jena University Hospital) before shipping to the saliva biomarker laboratory.

Stress parameter levels in saliva will be analyzed at Dresden LabService GmbH, Dresden, Germany, using commercial immunoassays from IBL International, Hamburg, Germany (i.e., Cortisol Saliva Luminescence ImmunoAssay (CLIA); and DHEA-S Saliva Enzyme-Linked Immunosorbent Assay (ELISA) following manufacturer's instructions. Saliva alpha-amylase will be analyzed following the method of Rohleider and colleagues (Rohleider, Nater et al. 2004).

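### The diurnal saliva profile is labelled resting state, but two to four of its four points follow the noon Cold Pressor Test, so it mixes resting level with stress response

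*Protocol*

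**What the plan says.** Section 4.2 sets the aim for saliva: "a secondary outcome is to demonstrate changes in decreased resting state stress parameters in saliva". The same sentence names reactivity to the CPT, measured in serum, as a further component. Under the resting-state heading, 4.2 lists both the awakening response (0 to 60 minutes) and the diurnal profile.

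Section 9.1.2 places the diurnal samples "at 4 time points at 3-hourly intervals over 12 hours at Baseline 1/ Day -1 and Visit 1/ Day 13", and the footnote to Table 4 confirms the restriction: "Only at Baseline 1 and Visit 1". Section 8.1 gives the sampling times for the two days as "3 hours, 6 hours, 9 hours and 12 hours after awakening at Day -1" and "3 hours, 6 hours, 9 hours and 12 hours after awakening at Day 13".

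Both days carry the stressor. For Baseline 1, 8.1 states "Around 12:00 at Day -1 a CPT will be conducted, before and afterwards blood samples will be collected"; for Visit 1, "Around 12:00 at Day 13 a CPT will be performed, blood samples will be collected", and the Visit 1 procedure list repeats "CPT around 12:00 including subjective pain and stress rating". Section 9.1.7 describes the CPT as the means of inducing stress and schedules it for every patient on these two days. Nothing in the protocol calls the later saliva samples post-stressor or limits the resting-state reading to the earlier ones.

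**The concern.** A sample taken after a deliberate stressor carries whatever remains of the response to it. If the product changes CPT reactivity, saliva collected after the CPT can differ between the arms even when their resting levels are the same. The protocol's own background makes this a live possibility: section 3.1 reports an earlier placebo-controlled trial in healthy volunteers in which salivary cortisol after an acute stressor was lower on the product.

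At stake is the interpretation of one secondary endpoint and of the planned correlations between stress and sleep parameters (4.2, 11.4.2). An effect reported as resting state could be an effect on stress reactivity. Elsewhere the protocol keeps the two apart: section 8.1 puts the resting EEG and heart-rate measurements about 15 minutes before the CPT, and 9.1.3 lists the EEG recordings before, during and after it separately. The saliva profile has no such separation.

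**Working it through.** The protocol prints no figure on this point, so there is none to reproduce. The check is clock arithmetic.

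**Inputs**
- CPT time C: about 12:00 on both days (8.1).
- Sample offsets k: 3, 6, 9 and 12 h after awakening (8.1; 9.1.2, Table 4).
- Awakening time w: not fixed for the laboratory nights. Inclusion criteria 3 and 4 (6.1) give a habitual bedtime of 21:00 to 01:00 and 6 to 9 h in bed. The earliest awakening is then 21:00 + 6 h = 03:00 and the latest 01:00 + 9 h = 10:00. I assume that laboratory awakening falls in this range.
- CPT response times in blood: 20 and 50 minutes after the CPT (9.1.7).

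**Step 1: which points follow the CPT.** A sample is taken at w + k. It follows the CPT when w + k > C, that is, when w > C − k. With C = 12:00 the limits for w are 09:00 (+3 h), 06:00 (+6 h), 03:00 (+9 h) and 00:00 (+12 h).

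| Awakening | Points after the CPT | Count |
|---|---|---|
| after 03:00, up to 06:00 | +9, +12 h | 2 of 4 |
| after 06:00, up to 09:00 | +6, +9, +12 h | 3 of 4 |
| after 09:00, up to 10:00 | +3, +6, +9, +12 h | 4 of 4 |

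At exactly 03:00 the +9 h sample coincides with the CPT and only +12 h follows it. Moving the CPT by 30 minutes moves every limit by 30 minutes.

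**Step 2: how long after.** Lag = w + k − 12:00, in minutes, for an assumed awakening at 05:00 to 08:00:

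| Awakening | +3 h | +6 h | +9 h | +12 h |
|---|---|---|---|---|
| 05:00 | −240 | −60 | 120 | 300 |
| 06:00 | −180 | 0 | 180 | 360 |
| 07:00 | −120 | 60 | 240 | 420 |
| 08:00 | −60 | 120 | 300 | 480 |

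**Step 3: overlap with the protocol's own response window.** The +6 h sample falls at 12:00 to 12:50 when w lies between 06:00 and 06:50. That is within the 50 minutes over which the protocol follows the CPT response in blood. For awakening between 05:00 and 08:00, no other diurnal point falls in that window.

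**Step 4: what is untouched.** For the latest awakening considered, the last awakening-response sample is at 10:00 + 60 min = 11:00, still before the CPT. These samples are taken at four visits, 5 × 4 = 20 per patient, and on Day 0 and Day 14 there is no CPT that day. The diurnal profile adds 4 × 2 = 8, of which 4, 6 or 8 follow the CPT when awakening falls in the same band of Step 1 at both visits.

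**The case against.** The strongest reply is that both arms have the same CPT on the same days at about the same clock time, so randomisation protects the comparison. That stands: the contrast is unbiased for the diurnal profile on a CPT day. It does not make that profile a resting-state one, and the label is what this point concerns.

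A second reply is that following the CPT is not the same as being altered by it. That also stands in part. The document gives no duration for a CPT effect in saliva, and its own blood sampling stops at 50 minutes. Most +9 h samples and all +12 h samples come hours later. Carry-over to them can be neither asserted nor excluded from the protocol.

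A third reply is that the analysis detail is deferred to the SAP and that all secondary analyses are exploratory (11.4.2). This limits the consequence. But the endpoint label, the sampling days and the CPT time are fixed in the protocol itself.

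A reader might go further and infer that the resting-state question cannot be answered at all. The document does not support this: the awakening samples at all four visits precede any same-day CPT, and so does +3 h for awakening before 09:00.

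A reader might also want to adjust for minutes since the CPT. With the CPT near noon, that quantity at each nominal time point is simply awakening time plus a constant (w + k − 12:00). It cannot separate recovery from time of day. At Visit 1, awakening time is also measured after randomisation, in a trial of a sleep treatment, so adjusting for it could remove or distort a treatment effect.

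**Conclusion.** The point holds for the diurnal profile and its label. For awakening after 03:00, two to four of its four points follow the CPT, so the profile mixes resting level with CPT response. No CPT-free day has a diurnal profile that could separate the two. A difference between arms in the later points cannot be attributed to the resting state.

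The exact count rests on a CPT at about 12:00 and on laboratory awakening within the 03:00 to 10:00 range implied by the habitual bedtimes and times in bed. How much the later values are altered is unknown; +6 h is the most exposed.

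This is a cheap improvement to a secondary, exploratory endpoint. The primary endpoint and the sample size do not depend on it.

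**What to change.** In sections 4.2, 9.1.2 and 11.4.2:

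- Base resting-state saliva conclusions on samples taken before the CPT by clock time: 0 to 60 minutes at all four visits, and +3 h where it precedes the CPT.
- Keep the full diurnal profile, but describe it as a CPT-day profile and summarise its post-CPT points separately from its pre-CPT points.
- Classify each sample by its actual time relative to the CPT. Section 13.3.1 already requires the date and time of trial measurements in source. Patients collect the saliva themselves (9.1.2), so the time used should be that of collection.
- Do not add minutes since the CPT as a covariate.

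The cost is wording in the protocol and the SAP, with no new samples or visits. The downside is that the resting-state conclusion rests mainly on morning samples, and the afternoon and evening course is reported only as seen on a CPT day. Moving the profile to Day 0 and Day 14 would avoid the CPT but is no simple substitute: trial treatment starts at midday on Day 0, so the later Day 0 samples would not be pre-treatment.
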